#### 6.8.2.2. TO ASSESS THE RELATION BETWEEN CLINICAL VARIABLES AND INITIAL RT-PCR RESULTS WITH THE INTERINDIVIDUAL DIFFERENCES IN THE IMMUNE RESPONSE IN EARLY, MID, AND LONG PERIODS OF IMMUNIZATION.

The incidence by SARS-CoV-2 will be linked to the sociodemographic, epidemiological, clinical and immunological information collected in the project. To analyze this, an exploratory bivariate analysis will be performed using the appropriate bivariate tests. Chi-squared tests will be used to find if there were any significant differences between the expected and the observed frequencies in categorical comparisons (e.g., the prevalence of symptoms per sex or clinical spectrum).. To study the differences between clinical spectrums and initial RT-PCR we will use ANOVAs or Kruskal-Wallis tests, after checking normality assumption using a Shapiro-test . Post-hoc analyses will be performed to find significant differences between clinical spectrum and immune response. Similarly, to look for differences in antibody levels between sex, either a t-test or a Mann-Whitney test will be performed.

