**Objectives:**

**Primary:** To consolidate a prospective cohort of Health Care Workers (HCWs) to generate epidemiological and clinical high quality data. This information will be relevant to improve health policies and clinical COVID-19 protocols. This cohort will also be used as an ongoing platform to implement SARS-CoV-2 research projects with particular emphasis on incidence rate, reinfection, vaccines, and long term immune response.

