**Secondary:**

1. To determine the kinetics of SARS-CoV-2 antibodies and cellular immune response in early, mid, and long periods of immunization.
2. To assess the relation between clinical variables and initial RT-PCR results with the interindividual differences in the immune response in early, mid, and long periods of immunization.
3. To analyze differentially expressed cytokines as biomarkers of disease progression in early, mid, and long periods of immunization.

**Methods and analysis:** Longitudinal, dynamic, prospective cohort study with a 12-month follow-up, which is being conducted in 4 primary-care centres and one hospital of Northern Metropolitana Nord of Barcelona (Spain). For now, the study consists of 1350 participants divided into 2 cohorts: 1) Healthy-Exposed HCWs: 675 not infected by SARS-CoV-2 (RT-PCR with a negative result and negative SARS-CoV-2 antibodies at baseline) and 2) Infected HCWs: 675 symptomatic participants (those with new persistent cough, temperature  $\geq 37.5^{\circ}\text{C}$ , anosmia, or ageusia or other compatible symptoms with COVID-19) or asymptomatic participants diagnosed by positive RT-PCR test and/or SARS-CoV-2 antibodies (IgM, IgG at baseline). Primary outcomes include: humoral and cellular immune response, quantitative antibodies to SARS-CoV-2, SARS-CoV-2 antibody levels related to progression phenotype, clinical spectrum of SARS-CoV-2, symptomatology, demographics and other variables that may be predictive of immune response.

**Follow-up:** baseline, 15 days, 1, 3, 6, 9 and 12 months.

**Findings to date:** Current literature has shown that the immune response is maintained for a minimum of 2 months. Nevertheless little is known about the association between the immune response and the progression phenotype of COVID-19.

**Future plans:** This prospective cohort offers the possibility to study associations between immune response and progression phenotype according to age and gender as well as long-term immune response. In turn, we will be able to examine possible cumulative effects, taking into account several

clinical variables. The study is ongoing and we plan to extend it to increase the size of the cohort until 2024.

**Ethics and dissemination:** The study is approved by the Ethics Committee (IDIAPJGol ref 20/067-PCV IGTP ref COV20/00660 (PI-20-205). Dissemination will occur through presentations at National and International conferences and publications in international peer-reviewed journals.

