## 6. METHODS

### 6.1. DESIGN:

Dynamic prospective study conducted in two cohorts of health care workers (HCW) (healthy and infected). Each cohort will include 675 participants.

Biological, clinical, psychological and social warning signs follow-up closely monitored during one year.

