#### 6.5. PROCEDURES

Participants entering the study after meeting exclusion/exclusion criteria (Table 1), give written informed consent (informed consent and patient information sheet, see Appendix 1) and they are assigned to a cohort (Figure 1). Cohorts are divided into:

- 1) Healthy pre-cohort: HCW exposed to but not infected with SARS-CoV-2, negative PCR-test or Ig M (N) and IgG (N)
- 2) Non-recent Infected cohort: HCW infected with SARS-CoV-2 (>15 days RT-PCR, positive)
- 3) Recent Infected cohort infected HCW : HCW with acute SARS-CoV-2 infection (<15 days RT-PCR, positive)

All participants undergo a standardised follow-up according to the specific cohort to which they are assigned (Table 2). At study entry, we record the following information: baseline socio-demographic

data, clinical data (symptoms), epidemiological data (contact with a positive and symptoms of COVID-19) (table 3), information on the work environment, data on the diagnosis of COVID-19 (previous biological samples taken and dates of sick leave due to COVID-19), use of personal protective equipment, previous health status and habits. At subsequent visits, epidemiological data, clinical data (symptoms) and vaccinations are recorded.

Finally, initial participant's cohort assignation is reviewed and reclassified on basis on laboratory results (RT-PCR test or SARS-CoV-2 antibodies IgM and IgG against the nucleocapsid (N)) in two final cohorts:

1) Health Care Workers Healthy Cohort (HCW\_H): This cohort includes HCW with negative laboratory test RT-PCR and SARS-CoV-2 antibodies IgM(N), and IgG(N).

2) Health Care Workers Infected Cohort (HCW\_I): This cohort includes HCW with positive laboratory test (RT-PCR and/or SARS-CoV-2 antibodies IgM and IgG) This cohort is subdivided into three categories according to the illness severity:

Asymptomatic or Presymptomatic Infection: Individuals with positive laboratory evidence of COVID-19 but no COVID-19 signs nor symptoms.

Mild-Moderate Illness: Individuals with positive laboratory evidence of COVID-19 who have any of the various signs and symptoms of COVID-19 (e.g., fever, cough, sore throat, malaise, headache, muscle pain, nausea, vomiting, diarrhea, loss of taste and smell) but who do not have shortness of breath, dyspnea, or abnormal chest imaging and home health care.

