**Primary Outcome Measure:**

1. Creation prospective cohort of health care workers

Include 675 exposed HCW participants and 675 infected HCW participants against SARS-CoV-2, cohorts will be compared at each time point in terms of sociodemographic, epidemiological, clinical, and immunological information available. an exploratory bivariate analysis will be performed using the tests of Chi Square, ANOVA, Kruskall-Walis, depending on the application conditions assumptions.

[Time Frame: Baseline, to 12 months after the beginning of the study]

2. Cohort description demografics ( age, sex, academic level, housing characteristics, work variables )

Descriptive analysis of the participants will be performed using the number and percentage for categorical variables, and mean and standard deviation or median and quartiles 1 and 3 for quantitative variables, an exploratory bivariate analysis will be performed using the tests of Chi Square, ANOVA, Kruskall-Walis, depending on the application conditions assumptions.

[Time Frame: Baseline, to 12 months after the beginning of the study]

2. Cohort description clinical spectrum (asymptomatic, mild-moderate illness, severe-critical)

Cohort comparison, an exploratory bivariate analysis will be performed using the tests of Chi Square, ANOVA, Kruskall-Walis, depending on the application conditions assumptions.

[Time Frame: Baseline, to 12 months after the beginning of the study]

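### Section 6.8.2.2 names an incidence analysis but gives only bivariate tests, which in a sample recruited by infection status describe association with infected status, not incidence or its risk factors

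*Combined protocol and SAP*

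**What the plan says.** Section 6.8.2.2 says "The incidence by SARS-CoV-2 will be linked to the sociodemographic, epidemiological, clinical and immunological information collected in the project". It continues that "an exploratory bivariate analysis will be performed using the appropriate bivariate tests", and goes on to name chi-squared, ANOVA, Kruskal-Wallis, t and Mann-Whitney tests. Section 6.8 defines no incident case, at-risk set, person-time, censoring rule or rate model.

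The cohorts are filled by infection status. Section 6.1 says "Each cohort will include 675 participants", and the primary outcome in Section 6.6.2 reads "Include 675 exposed HCW participants and 675 infected HCW participants against SARS-CoV-2". In Section 6.5 the infected pre-cohorts take workers more than 15 days from a positive RT-PCR as well as those within 15 days of one.

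On when status is fixed, the abstract describes the healthy cohort as "675 not infected by SARS-CoV-2 (RT-PCR with a negative result and negative SARS-CoV-2 antibodies at baseline". Section 6.5 says "initial participant's cohort assignation is reviewed and reclassified on basis on laboratory results", with no time limit.

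The primary aim describes the cohort as a platform for research projects "with particular emphasis on incidence rate, reinfection, vaccines, and long term immune response". Section 6.3 runs recruitment from 31 March 2020 to an estimated 15 June 2021.

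**The concern.** An incidence needs people free of infection at the start, a count of new infections among them, and the time over which they were observed. The pooled sample provides the first for only half of its members. In the other half, infection was a condition of entry. A bivariate test of infected against not infected therefore mixes infections present at recruitment with any that arise in follow-up, and gives no weight to how long, or in which wave, a person was at risk.

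At stake is how the results are read. Incidence rate is the first item of emphasis for the platform, Section 6.2.1 describes sampling as random, and Section 6.4 calls the sample representative. A reader could take a pooled association as a finding about the risk of acquiring infection. Factors related to when someone was infected or recruited (wave, protective equipment, vaccination) are the most exposed to this confusion.

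**Working it through.** **The plan's own figure.** Section 6.4 gives 522 per group for 90% power at η² = 0.01 and α = 0.05. With f² = 0.01/0.99 = 0.0101 and the noncentral F distribution for two groups, the smallest n is 522 (power 0.9005). Dividing by 0.90 for dropout gives 580. Both figures reproduce, but they concern a difference in means and say nothing about incidence.

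**Entry window.** 31 March 2020 to 31 March 2021 is 365 days, and 76 more lead to 15 June 2021: 441 days. Section 6.2.1 refers to the first, second and third waves, and Section 6.5 records vaccination at later visits. Even if everyone were followed for the same 12 months, those months would fall in different epidemic periods.

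**What the 1:1 quota does and does not distort.** Assume a binary factor held by half the source population and a true risk ratio of 2.

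- Risks 5% and 10% (mean 7.5%). Infected with the factor: 675 × 0.5 × 0.10/0.075 = 450; without: 225. Not infected with the factor: 675 × 0.5 × 0.90/0.925 = 328.4; without: 346.6. Infected shares are 450/778.4 = 57.8% and 225/571.6 = 39.4%, ratio 1.47. Sample odds ratio: (450 × 346.6)/(225 × 328.4) = 2.11. Population odds ratio: (0.10/0.90)/(0.05/0.95) = 2.11.
- Risks 20% and 40%. Shares are 60.9% and 36.8%, ratio 1.65. The odds ratio is 2.67 in both sample and population.

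The quota alone leaves the odds ratio intact. The shares are not risks, and their ratio is not a risk ratio. The odds ratio still refers to being infected by the time of classification, with old and new infections together.

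**When membership is fixed.**

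- Abstract: status at baseline.
- Section 6.5: initial assignment reclassified on laboratory results, timing not given.
- Tables 2 and 5: healthy participants with antibodies at Visit 4 are still listed under the healthy label at later visits.

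These do not settle whether a converter changes cohort.

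**What the baseline negatives could support.** The 95% half-width is 1.96 × √(p(1−p)/675), before dropout:

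| Assumed 12-month risk | Expected converters | Half-width (points) |
|---|---|---|
| 2% | 13.5 | 1.1 |
| 5% | 33.8 | 1.6 |
| 10% | 67.5 | 2.3 |
| 20% | 135 | 3.0 |

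**False conversions.** Section 6.6 gives the ELISA specificity as 93.3%. In 675 true negatives, one round would give 675 × 0.067 ≈ 45 false positives. That exceeds the 34 true converters expected at an assumed 5% risk. It treats the stated figure as applying to one result per person per round; repeat errors in the same person may be correlated.

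**The case against.** The plan can be defended on several grounds, and some of the defence stands.

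- No sentence says that incidence will be the number infected divided by 1350. A reader might infer that the reported incidence will simply be the recruitment quota, or the quota shifted by converters. The documents do not support that, because they state no estimator. The baseline negatives are retested, so a valid incidence is obtainable. What stands against the plan is that it does not say this is what will be done.
- A reader might also infer that converters leave the healthy cohort and so leave it with no observed incidence. That is only one reading of Section 6.5. The abstract's baseline definition and the visit tables point the other way. Only the missing timing can be criticised.
- The quota does not invalidate chi-squared tests of association with infected status. This stands, as the odds ratios above show. It does not separate infections present at entry from new ones, nor account for calendar time.
- Incidence is not a listed primary or secondary outcome. The analysis is called exploratory, within a section about immune response. This stands and lowers the priority.
- A person-time analysis is not free of difficulty. Conversions will often be known only to lie between visits about three months apart. Section 6.6 mentions fortnightly RT-PCR, but the visit tables show none for healthy workers at Visits 5 to 9. With the limited specificity, this shapes the fix but does not remove the need for it.

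**Conclusion.** The point holds in a limited form. The bivariate tests in Section 6.8.2.2, applied to infected against not infected, can describe association with infected status. They cannot yield an incidence or identify its risk factors, because the cohorts are formed by infection status, infections at entry are included, and time at risk and calendar period are left out. Separately, the abstract and Section 6.5 must be reconciled on whether later converters change cohort.

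No numerical bias can be attached to the plan as written. The share ratios of 1.47 and 1.65 rest on assumed risks and show only what would follow if pooled shares were read as risks. The precision figures rest on assumed 12-month risks of 2% to 20% and on no dropout. The sample size and the immune-response analyses are unaffected. This is a cheap improvement to an exploratory analysis.

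**What to change.** Amend Sections 6.5 and 6.8.2.2 as follows.

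1. Define cohort membership by the baseline laboratory result, and bring the abstract, Section 6.5 and the visit tables into line.
2. Restrict the incidence analysis to workers negative at baseline. Count person-time from enrolment to the first positive or the last negative test. Count follow-up after conversion as infected follow-up.
3. For this analysis, replace the bivariate tests with a rate or time-to-event model that accounts for calendar period and vaccination, for example Poisson regression, or Cox regression on calendar time with delayed entry.
4. Require confirmation of serology-only conversions from results already collected: an RT-PCR, including those in the electronic records listed in Section 6.7, or a repeat positive. State that conversions found only at scheduled visits are interval-censored, and how that will be handled.
5. Keep the pooled bivariate tests if wanted, described as association with infected status and reported as odds ratios.

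The cost is a few paragraphs of text and the preparation of a dated person-time data set, with no new recruitment or sampling. Fewer participants and events enter the incidence analysis, so its estimates will be less precise than the pooled total of 1350 might suggest. The confirmation rule may also drop some true conversions that lack a second result.

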**Secondary Outcome Measures:**

4. Kinetics of SARS-CoV-2. IgM Nucleocapside

IgM (nucleocapside) ELISA kits (Inmunodiagnostic Limited ©). Positivity thresholds were provided by the assay manufacturers and were considered positive with an index value greater than 1.1, indeterminate from 0.9 to 1.1 and negative if <0.9 index units

[Time Frame: Baseline, 7 days, 15 days, 3, 6, 9 and 12 months after the beginning of the study]

5. Kinetics of SARS-CoV-2. IgG Nucleocapside

IgG (nucleocapside) ELISA kits (Inmunodiagnostic Limited ©). Positivity thresholds were provided by the assay manufacturers and were considered positive with an index value greater than 1.1, indeterminate from 0.9 to 1.1 and negative if <0.9 index units

[Time Frame: Baseline, 7 days, 15 days, 3, 6, 9 and 12 months after the beginning of the study]

6. Kinetics of SARS-CoV-2. IgG Spike

IgG (spike). ELISA kits DECOV1901 (Demeditec Diagnostics GmbH©). Positivity thresholds were provided by the assay manufacturers and were considered positive with an index value greater than 40, indeterminate from 32 to 40 and negative if <32 UI/ml

[Time Frame: Baseline, 7 days, 15 days, 3, 6, 9 and 12 months after the beginning of the study]

7. Kinetics of SARS-CoV-2. T-Cell

SARS-CoV-2 specific CD4+ and CD8+ T-cell responses we performed an IFN $\gamma$  ELISPOT assay. Wells will be considered positive if they contained at least 50 spot-forming cells per 10^6 PBMCs above the background level (2X mean + 3Xstandard deviation).

[Time Frame: Baseline, 7 days, 15 days, 3, 6, 9 and 12 months after the beginning of the study]

8. To assess the relation between clinical variables and initial RT-PCR results in the whole sample and by sex.

To study the differences between clinical spectrums and initial RT-PCR we will use ANOVAs or Kruskal-Wallis tests, after checking normality assumption using a Shapiro-test

[Time Frame: Baseline, to 12 months after the beginning of the study]

9. To analyse the relation between clinical variables and the interindividual differences in the immune response in early, mid, and long periods of immunization in the whole sample and by sex

To study the differences between clinical spectrums and immune response in early period we will use ANOVAs or Kruskal-Wallis tests, after checking normality assumption using a Shapiro-test . Similarly, to look for differences in antibody levels between sex, either a t-test or a Mann-Whitney test will be performed.

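### The unadjusted comparison of initial RT-PCR across clinical spectrums can reflect entry route and delay to the swab rather than severity

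*Combined protocol and SAP*

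**What the plan says.** Outcome 8 in section 6.6.2 is "To assess the relation between clinical variables and initial RT-PCR results in the whole sample and by sex". Section 6.8.2.2 gives the method: "To study the differences between clinical spectrums and initial RT-PCR we will use ANOVAs or Kruskal-Wallis tests", after a normality check. The same section introduces its approach with "an exploratory bivariate analysis will be performed using the appropriate bivariate tests". Neither place restricts, stratifies or adjusts for how or when a worker entered. Section 6.6.2 mentions confounding factors in general terms but names no method.

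Section 6.5 sets the entry rules. The two infected pre-cohorts are "Non-recent Infected cohort: HCW infected with SARS-CoV-2 (>15 days RT-PCR, positive") and "HCW with acute SARS-CoV-2 infection (<15 days RT-PCR, positive"). After reclassification on laboratory results, the final infected cohort is wider: "This cohort includes HCW with positive laboratory test (RT-PCR and/or SARS-CoV-2 antibodies IgM and IgG"). The three clinical spectrum classes are subdivisions of this final infected cohort. The abstract likewise admits "asymptomatic participants diagnosed by positive RT-PCR test and/or SARS-CoV-2 antibodies (IgM, IgG at baseline").

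The documents do not say whether initial RT-PCR means the diagnostic swab or the first study swab, nor whether it is a positive/negative result or a quantity.

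**The concern.** The variable being compared also helps to decide who is in the comparison. A worker enters the infected cohort by a positive RT-PCR or by antibodies. One whose initial RT-PCR is negative got there through serology, or was swabbed long enough after infection for viral RNA to have gone. Both are features of recruitment and timing.

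These features may well differ by severity. Symptoms bring people to a swab, and section 4 describes workers with symptoms or high-risk contacts confined while they wait for RT-PCR results. A worker without symptoms is recognised as infected only by a laboratory result, which may be an antibody result at baseline. If asymptomatic workers more often enter by serology or with an older infection, their RT-PCR positivity will be lower whatever the biology.

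At stake is part of secondary aim 2: the report could present a difference in initial RT-PCR between severity classes as a clinical finding when recruitment alone can produce it. More participants would not remove the bias; they would only make it more likely to be significant.

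**Working it through.** **1. The plan's own figure.** Section 6.4 gives 522 per group for a two-group F test (alpha 0.05, power 90%, eta squared 0.01). With f² = 0.01/0.99, the noncentral F power at 522 per group is 0.9005, and 522/0.90 = 580 after dropout. Both figures reproduce. They concern two cohorts and do not address a three-class comparison within the infected.

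**2. The two readings of initial RT-PCR.**
- *Diagnostic swab:* both infected pre-cohorts are positive by definition, so a negative marks a worker counted as infected through antibodies.
- *First study swab:* the result depends on days since infection. In Table 2 the non-recent group has no visit 1, and its first listed study RT-PCR is at visit 4.

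On either reading the result carries entry route or delay.

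**3. Can this alone produce a difference?** From the documents: 675 infected workers, three severity classes, test level 0.05. The following are assumptions, because the documents are silent:
- severity mix (asymptomatic / mild-moderate / severe-critical) 25/65/10%, with alternatives 10/80/10 and 40/55/5;
- share recently infected at the swab, by class: 60/60/60, 50/60/60, 40/60/60 or 30/60/70%;
- positivity, recent against non-recent: 95% vs 30%, 90% vs 50%, or 90% vs 80%, identical in every severity class, so severity has no effect.

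Expected positivity in a class = recent share × recent positivity + (1 − recent share) × non-recent positivity. In the central case (mix 25/65/10, recent share 40/60/60, positivity 95% vs 30%):
- asymptomatic: 0.40 × 0.95 + 0.60 × 0.30 = 0.56
- other classes: 0.60 × 0.95 + 0.40 × 0.30 = 0.69
- pooled: 0.25 × 0.56 + 0.75 × 0.69 = 0.6575

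The noncentrality on 2 degrees of freedom is 675 × [0.25 × (0.56 − 0.6575)² + 0.75 × (0.69 − 0.6575)²] / (0.6575 × 0.3425) = 9.5, which gives a rejection probability of 0.79. Simulation of the Kruskal-Wallis test on the binary result (2,000 runs per scenario) agrees: 79%. A Cochran-Mantel-Haenszel test stratified by recent/non-recent rejects in 5.6%.

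Across all severity mixes and positivity pairs:

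| Recent share by class | Planned test rejects |
|---|---|
| 60/60/60% | 4.4–5.9% |
| 50/60/60% | 4.5–33% |
| 40/60/60% | 7–87% |
| 30/60/70% | 10–99.8% |

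The stratified test stays at 4.1–6.2% in all scenarios. It does so partly by construction: positivity was made constant within each delay class. With no upper limit on the non-recent class, real data could keep some bias within that stratum.

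**The case against.** The strongest reply is that the bias is conditional and its size cannot be shown. That stands. With equal delay mixes the planned test keeps its level, and with unequal mixes the rejection rate runs from about 4.5% to 99.8% depending on inputs that nobody has. Section 4 also counts high-risk contacts among those awaiting RT-PCR, so some symptom-free workers were tested early. Section 6.6 speaks of RT-PCR every two weeks, although the visit tables list no such swabs; those passages must be reconciled. The analysis is labelled exploratory, which lowers the stakes but does not remove the bias.

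Four stronger readings are tempting, and the documents do not support them.
- *A difference must appear.* It needs route or delay to vary with severity, which is plausible but not documented.
- *The whole-sample comparison is distorted because healthy workers are RT-PCR negative by definition.* The phrase most naturally means both sexes pooled. Spectrum classes exist only within the infected, so healthy workers have no class to be compared in.
- *RT-PCR-negative infected workers come mainly from the healthy pre-cohort.* Table 2 also foresees recent-infected workers with negative RT-PCR at visit 1 and before, and no proportions are given.
- *The false association would be extremely significant.* Choosing a large gap in positivity and quoting its p-value shows only that the test finds the gap that was put in.

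**Conclusion.** The point holds in conditional form. As written, outcome 8 and section 6.8.2.2 can yield a biased comparison, because initial RT-PCR is tied to how and when a worker entered and nothing in the analysis separates this from severity. The conclusion about mechanism rests on the entry definitions in section 6.5 and on the lack of any adjustment; it holds whether the swab meant is the diagnostic one or the first study one.

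The size is unknown. The 79% in the central case is an illustration that depends wholly on the assumed severity mix, delay mix and positivity rates, and it treats the result as positive/negative. It shows that a moderate imbalance in delay can be enough; it does not predict what this cohort will show. For an exploratory secondary outcome this is a change that should be made, and it is cheap. It does not threaten the study.

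**What to change.** In section 6.8.2.2 and outcome 8:

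1. State which swab is the initial RT-PCR, how it is dated and on what scale it is analysed.
2. Limit the comparison to the infected cohort. Stratify by entry pre-cohort (recent, non-recent, reclassified from healthy) and by time to the swab from symptom onset or, without symptoms, from the first positive test.
3. Report serology-only, RT-PCR-negative entrants separately and descriptively.
4. For a positive/negative result, replace ANOVA by a stratified categorical test such as Cochran-Mantel-Haenszel.
5. State that the pooled unadjusted difference will not be interpreted as an effect of severity.
6. Reconcile Tables 2 and 5 on the first study RT-PCR: Table 5 lists it at visit 1 for infected workers, while Table 2 gives the non-recent group no visit 1 (the extracted tables may be imperfect).

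The choice in item 1 matters. If the diagnostic swab is meant, a positive/negative result has no variation once serology-only entrants are set apart, and a descriptive table by entry route is all that remains. The stratified test is informative for the first study swab. A cycle-threshold measure is possible but not required; the documents list only an RT-PCR result.

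The cost is mainly wording. Sections 6.5 and 6.6 already provide the pre-cohort, information on previous samples and the symptom-onset date. The downside is smaller strata and less precision, especially for asymptomatic workers, who have no onset date and whose true delay since infection stays uncertain.
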